The estimates for treatment effect may be obtained by LANCOVA in the same manner as described in Section 6.1.2 where the change from baseline of a corresponding score (ie, activity or damage score) will be used as a dependent variable. Estimates and the confidence intervals for treatment effect will be presented for each of these methods. Accompanying plots may also be provided.

A supportive analysis that includes subjects with skin disease (baseline CDASI activity score of 14 or greater) in Stage 3 (FAS3) may also be performed for the CDASI activity and damage score using the models specified in Section 6.1.2.

6.3.3. Exploratory Efficacy Endpoints in Stage 3

Exploratory efficacy endpoints will be summarized in Stage 3 in the same manner as the corresponding endpoints in Stage 1, Stage 2, or Amended Stage 2 using the appropriate Stage 3 analysis set (Section 6.1.3; Section 6.2.3). The only newly added PRO to Stage 3 is the FACIT-F. The average ranking across all questions of the FACIT-F for each patient will be summarized in the same manner as the PhGA (see Sections 6.1.3.4 and 9.4.9).

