2.3. Amended Stage 2, Objectives and Endpoints

Pri	mary Objective(s):	Primary Endpoint(s):	
	To estimate the efficacy of PF-06823859 in adult participants with moderate to severe DM across Stage 1 and Stage 2.	Change from baseline in CDASI activity sco at Week 12.	ore
Sec	condary Objective(s):	Secondary Endpoint(s):	
•	To estimate the efficacy of PF-06823859 over time across Stage 1 and Stage 2.	• Absolute values and change from baseline of CDASI activity and CDASI damage scores a all scheduled time points. (Exception: The change from baseline in CDASI activity score at Week 12 is a primary endpoint).	f at re
•	To determine the safety, and tolerability, of PF-06823859 across Stage 1 and Stage 2.	• Incidence of adverse events (AEs) laboratory abnormalities, changes in vital signs, and electrocardiogram (ECG) findings.	у
Ex	ploratory Objectives (s)	Exploratory Endpoints(s)	
•	To characterize pharmacokinetics (PK) of PF-06823859 across Stage 1 and Stage 2.	Plasma concentration of PF-06823859.	
•	To characterize pharmacodynamics (PD) effects of PF-06823859 across Stage 1 and Stage 2. To estimate the effects of PF-06823859 on the Physician Global Assessment (PhGA, VAS) across Stage 1 and Stage 2.	 Absolute values and change from baseline in the values of selected biomarkers (Gene signature panel in blood and tissue; Human Myxovirus A (MXA), interferon gamma-induced protein 10 (IP-10), CCI highly sensitive C-reactive protein, (hsCRP) muscle and bone blood biomarkers, autoantibody concentrations in serum/plasma at all scheduled time points. Absolute values and change from baseline in the values of the PhGA, VAS at all schedule time points. 	n), a) n ed
		• Absolute values and change from baseline in the values of PROs including the Patient	1

• To estimate the effects of PF-06823859 on patient-reported outcomes (PROs) over time across Stage 1 and Stage 2.	Global Assessment (PtGA), the Health Assessment Questionnaire – Disability Index (HAQ-DI), the 5-D Pruritus Scale, CCI , the Short Form (SF-36 v2 Acute), the Dermatology and Life Quality Index (DLQI) and the European Quality of Life Five Dimension, Five Level Scale (EQ-5D-5L) & EQ Visual Analogue Scale (EQ-VAS) at all scheduled time points.
• To estimate the effects of PF-06823859 on CDASI sub-scores across Stage 1 and Stage 2.	• Absolute values and change from baseline values of the sub-scores of CDASI activity and CDASI damage scores at all scheduled time points.

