For the comparison of 150 mg PF-06823859 and placebo, assuming a SD of 8 and assuming a pooled sample size of approximately 10 and 11 completers respectively across the two Stages, we expect the half length of the 90% CI to be 5.75. For the comparison of 600 mg PF-06823859 and placebo, assuming a SD of 8 and assuming a pooled sample size of approximately 21 and 11 completers respectively across the two Stages, we expect the half length of the 90% CI to be 4.90.

No p-values will be presented for the comparisons listed in the objectives and endpoints of Section 2.2 for Stage 2.

9.1.3. Sample Size Determination in Stage 3

The major efficacy endpoint of interest in Stage 3 is the TIS,³¹ which is a continuous measure ranging from 0 to 100. The treatment effect is defined as the difference in mean TIS between the active and placebo treatment groups at Week 12. The standard deviation in TIS at Week 12 is estimated to be between 15 and 25 units.^{32,33}

The DM muscle disease cohort will enroll between 8 and 16 participants randomized 1:1 to active and placebo. Table 3 shows the estimated half widths of the 90% confidence intervals for the difference in mean TIS between the PF-06823859 600 mg arm and the placebo arm at Week 12 across a range of standard deviations and number of completers. For example, if 10 participants (5 active, 5 placebo) complete the Week 12 assessment and the SD of the TIS is 20, the estimated half width of the 90% confidence interval is approximately 20.8.

No p-values will be presented for the comparisons listed in the objectives and endpoints of Section 2.4 for the DM muscle cohort.

Table 3.	Estimated Half-widths of 90% Confidence Intervals for the Difference in
	TIS between Active and Placebo at Week 12

Number of completers (active: placebo)	Assumed SD of TIS	Half width of 90% CI
	15	17.4
8 (4:4)	20	23.3
	25	29.1
	15	15.6
10 (5:5)	20	20.8
	25	26.0
	15	14.2
12 (6:6)	20	19.0
	25	23.7
	15	13.2
14 (7:7)	20	17.6
	25	22.0
	15	12.3
16 (8:8)	20	16.4
	25	20.6

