Appendix 10. EQ-5D-5L AND EQ-VAS

[Health Questionnaire
1	
[English version for the USA

USA (English) © 2009 EuroOck Group EQ-5D™ is a trade mark of the EuroOck Group

PFIZER CONFIDENTIAL Page 166

Under each heading, please check the ONE box that best descr	ibes your health TODAY.
MOBILITY	
I have no problems walking	
I have slight problems walking	
I have moderate problems walking	
I have severe problems walking	
I am unable to walk	
SELF-CARE	
I have no problems washing or dressing myself	
I have slight problems washing or dressing myself	
I have moderate problems washing or dressing myself	
I have severe problems washing or dressing myself	
I am unable to wash or dress myself	
USUAL ACTIVITIES (e.g. work, study, housework, family or leisure activities)	
I have no problems doing my usual activities	
I have slight problems doing my usual activities	
I have moderate problems doing my usual activities	
I have severe problems doing my usual activities	
I am unable to do my usual activities	
PAIN / DISCOMFORT	
I have no pain or discomfort	
I have slight pain or discomfort	
I have moderate pain or discomfort	
I have severe pain or discomfort	
I have extreme pain or discomfort	
ANXIETY / DEPRESSION	
I am not anxious or depressed	
I am slightly anxious or depressed	
I am moderately anxious or depressed	
I am severely anxious or depressed	
I am extremely anxious or depressed	

2

USA (English) © 2009 EuroQoLGroup EQ-5D™ is a trade mark of the EuroQoLGroup

USA (English) © 2009 EuroGol Group EQ-50™ is a trade mark of the EuroGol Group

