The sensitivity analyses from Stage 1 (Section 6.1.1.2) may be repeated using the pooled data from Stage 1, Stage 2, and Amended Stage 2 using the PFASS. For these sensitivity analyses, estimates and CIs may be produced. No p-values will be produced.

The analysis for the CDASI-A in Section 6.2.1.1 using PFASS may be repeated adjusting for subjects meeting protocol discontinuation criteria for use of prohibited medications as an intercurrent event (if any). Data from visits occurring after meeting discontinuation criteria for use of prohibited medications will be censored from this analysis.

6.2.1.4. Supportive Analyses in Stage 2 and Amended Stage 2

Supportive analyses may be reported in Stage 2. For one supportive analysis, summary statistics will be reported by treatment sequence and visit for the participants in the FASA2 from baseline to Week 28. The sample size, mean, standard deviation, median, minimum and maximum will be presented.

6.2.2. Secondary Endpoint(s) in Stage 2 and Amended Stage 2

The analyses and summaries of the secondary endpoints in Stage 2 will be the same as those in Stage 1 (Section 6.1.2) except that they will be conducted for the data across Stage 1, Stage 2, and Amended Stage 2 and use the appropriate Stage 2 analysis set. No p-values will be presented for these analyses.

6.2.3. Exploratory Efficacy Endpoints in Stage 2, and Amended Stage 2

The analyses and summaries of the exploratory efficacy endpoints in Stage 2 will be the same as those in Stage 1 (Section 6.1.3) except that they will be conducted for the data across Stage 1, Stage 2, and Amended Stage 2 and use the appropriate Stage 2 analysis set.

Statistical summaries will stratified by treatment group. No p-values will be presented for these analyses.

Percent change from baseline in the CDASI activity score will also be analyzed and reported in the same manner as the change from baseline CDASI activity score as described in Section 6.2.1.1.

For PROs newly added to Amended Stage 2 that were not collected in Stage 2, including the PtGA, HAQ-DI, CCI and EQ-5D-5L & EQ-VAS, descriptive statistics will be provided at each visit using the FASA2 and reported by treatment group. The reporting results for these PROs will be the same as those in Section 6.1.3.4, with some additional details provided below:

- For the PtGA and EQ-VAS scores, a single score summarizes each of the corresponding patient-reported outcomes (see Sections 9.4.5 and 9.4.8).

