- For the CCl each of the three questions will be summarized by a single score (see Section 9.4.7).
- For the EQ-5D-5L, the summed number of checked boxes under each of the five sections will be reported (see Section 9.4.8).
- For the HAQ-DI, a single averaged score summarizes each of the corresponding patient-reported outcomes under the eight sections (see Section 9.4.6). In sections of the HAQ-DI relating to aids or devices or help from another person, each checkable box will be treated as binary data and summarized with proportions and frequency counts. A single score summarizes the severity of pain VAS.

6.3. Analyses and Summaries During Stage 3

6.3.1. Primary Endpoint in Stage 3

The primary endpoint in Stage 3 includes the incidence of adverse events (AEs) laboratory abnormalities, changes in vital signs, and electrocardiogram (ECG) findings. All safety summaries and analyses will be performed as specified in Section 6.7.

6.3.2. Secondary Endpoint(s) in Stage 3

6.3.2.1. Total Improvement Score in Stage 3

- Analysis population: FAS3.
- Analysis time points: Week 12 and intermediate scheduled time points.
- Analysis methodology: The TIS at post baseline visits are scored relative to baseline and the TIS at baseline is 0 by definition; thus all analyses are performed directly on the TIS. The estimates of the treatment effect from baseline to Week 12 will be obtained by MMRM where the TIS will be used as a dependent variable. This model uses fixed effects for treatment, time (visit), treatment by time, and a random effect for subject, Due to the unknown nature of the longitudinal data, different covariance

structures among repeated measures will be examined based on model diagnostics starting with the unstructured variance-covariance model.

- Supporting objective: Secondary objective.
- Reporting results: The absolute value of the TIS at each post baseline visit will be summarized by the following descriptive statistics:
 - The sample size, mean, standard deviation, median, minimum and maximum will be presented for each treatment arm (active and placebo).
 - The LS means, 90% confidence interval for the LS means, difference between the LS means of treatment groups (active treatment arm placebo) and the corresponding 90% confidence interval for the estimate. Plots of this data will also be presented. No p-values will be computed for the analysis in this stage.

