9.4.8. EQ-5D-5L & EQ-VAS

The EQ-5D-5L contains five sections, including mobility, self-care, usual activities, pain/discomfort, and anxiety/depression (see Appendix 10 of the protocol). Each of the five sections will be summarized by the number of checked boxes under their respective headers.

The EQ-VAS ranges from 0 to 100, where 100 is the best (ie, most healthful) score.

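### The SAP's box count for the EQ-5D-5L gives 1 for every completed dimension and a change from baseline of 0, because the form allows one box per heading

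*SAP*

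**What the plan says.** Two SAP sections give the scoring rule, in the same sense. Section 6.2.3 (exploratory endpoints, Stage 2 and Amended Stage 2): "For the EQ-5D-5L, the summed number of checked boxes under each of the five sections will be reported". Section 9.4.8, the instrument description it points to: "Each of the five sections will be summarized by the number of checked boxes under their respective headers".

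The form is in protocol Appendix 10. Its instruction begins "Under each heading, please check the ONE box that best", and each of the five headings lists five ordered options, from no problems to the worst level.

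The endpoint in protocol section 2.3 is the absolute value and the change from baseline of a list of patient-reported outcomes that ends with the "European Quality of Life Five Dimension, Five Level Scale (EQ-5D-5L) & EQ Visual Analogue Scale (EQ-VAS) at all scheduled time points". Section 2.4 has the same item for Stage 3. For outcomes new in Amended Stage 2, SAP 6.2.3 applies the reporting of SAP 6.1.3.4: sample size, mean, SD, median and range by visit, for absolute values and for change. For Stage 3, SAP 6.3.3 says of the exploratory outcomes that they "will be summarized in Stage 3 in the same manner as the corresponding endpoints in Stage 1, Stage 2, or Amended Stage 2".

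**The concern.** On a single-choice item, the information lies in which option was ticked. How many were ticked is fixed by the instruction on the form. A programmer who follows 6.2.3 and 9.4.8 literally would fill the EQ-5D-5L tables with a constant: mean 1, SD 0, change 0, in every arm and at every visit. The plan names EQ-5D-5L values and change from baseline as an endpoint in two cohorts, and participants complete the form repeatedly. As written, the dimension part of that endpoint could not show improvement, worsening or any difference between arms.

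**Working it through.** The plan gives no figure to reproduce here, since no test, power or sample size is attached to this endpoint. The check applies the stated rule to every answer the form permits.

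**Inputs**
- Five dimensions, five levels each, one box per heading (protocol Appendix 10).
- Summary = number of checked boxes under each heading (SAP 6.2.3 and 9.4.8).
- Scheduled assessments: Day 1 and Weeks 1, 4, 16, 28 and 40, which is 6 (Schedules of Activities, Amended Stage 2 and Stage 3). None falls at Week 12 or Week 24.

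**One dimension.** Let b_k = 1 if box k is ticked and 0 otherwise, k = 1 to 5. The rule gives b_1 + b_2 + b_3 + b_4 + b_5. With one box ticked this is 1, whatever the level.

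**All five dimensions.** There are 5^5 = 3,125 complete profiles. Each gives (1, 1, 1, 1, 1), total 5. The SD between participants is 0.

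**Change from baseline.** A dimension has 5 × 5 = 25 possible pairs of baseline and follow-up level. Each gives 1 − 1 = 0. A participant who moves from the worst to the best level on all five dimensions improves by 5 × (5 − 1) = 20 levels and shows a change of 0.

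**Summing over participants.** If the word summed means adding boxes across participants, the total under each heading is the number who answered (5, 10 or 20 for n = 5, 10 or 20), again whatever their health.

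**What could vary.** A blank dimension counts 0 and an invalid double tick counts 2. Variation would then reflect missing or faulty answers.

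**With the level coded 1 to 5.** Each dimension takes 5 distinct values, and change runs from −4 to +4.

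**Extent per participant**

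| Route | Assessments | Dimension scores, all 1 | Changes from baseline, all 0 |
|---|---|---|---|
| Stays through Week 40 | 6 | 6 × 5 = 30 | 5 × 5 = 25 |
| Enters the extension after Week 24 | 4 (Day 1, Weeks 1, 4, 16) | 4 × 5 = 20 | 3 × 5 = 15 |

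**The case against.** The strongest reply is that this is loose drafting and that a tally of each response level was meant. Mean, SD and change from baseline make no sense for a constant. Protocol 9.2.3.3 likewise expects the Stage 3 values of the EQ-5D-5L to be summarised descriptively at each visit. That makes a slip more likely than a deliberate choice, and it lowers the severity. It does not supply the missing rule, for three reasons:
- The count is stated per section, not per level.
- The next bullet in 6.2.3, on HAQ-DI aids and devices, shows how the authors write a box-by-box tally: "each checkable box will be treated as binary data and summarized with proportions and frequency counts".
- SAP 9.4.3 shows how they write level scoring: single-item domains of the 5D itch scale take the value attached to the chosen response.

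Neither form is used for the EQ-5D-5L. A frequency table would not fit the 6.1.3.4 statistics either, so the text needs correcting whichever was intended.

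It can also be said that the ticked levels may still appear in listings, since SAP 6.7.8 lists any other data on the database, and that a column of 1s would be noticed at first table review. Both are fair, and both bear on consequence only. The copy reviewed lacks the text of protocol 7.7.5, the EQ-5D-5L description. That absence is not counted against the plan, but a scoring rule there cannot be excluded.

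A reader might infer that the FACIT-F has a parallel scoring fault, because SAP 6.3.3 and 9.4.9 average its items without mentioning reversal. The documents do not support that. Protocol 7.7.8 already requires reversal where appropriate, and the average of the 13 reversed items is the 0 to 52 sum divided by 13.

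**Conclusion.** The rule is wrong as written, and the matter is minor. Taken literally, the planned EQ-5D-5L dimension summaries carry no health information in Amended Stage 2 or Stage 3, at up to 6 assessments per participant, or 4 for those who move to the extension study. This rests on completed dimensions with one tick each and on the SAP text as it stands.

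Three stronger readings should be resisted. A reader might infer that the whole EQ-5D-5L endpoint or its data are lost. They are not: the level ticked is on the form, and the EQ-VAS is scored on its own ("For the PtGA and EQ-VAS scores, a single score summarizes each of the corresponding patient-reported outcomes"). A reader might also infer damage to the trial's conclusions. The endpoint is exploratory and descriptive, with no p-values, and CDASI, TIS and safety do not depend on it. Finally, a reader might multiply up to cohort totals. For Stage 3, with 8 to 16 participants, that gives 8 × 30 = 240 to 16 × 30 = 480 scores. These are maxima, because they assume that nobody leaves for the extension study and no assessment is missed.

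**What to change.** In SAP 6.2.3 and 9.4.8, replace the box count with: *Each EQ-5D-5L dimension is coded 1 to 5 by the level checked (1 = no problems, 5 = worst level). The number and percentage of participants at each level, and a shift table of level from baseline, are reported by dimension, visit and treatment group, in place of the Section 6.1.3.4 mean/SD summaries for these items.*

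SAP 6.3.3 then carries the corrected rule into Stage 3 without further change. No FACIT-F wording is needed.

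The cost is one passage of text in two places and the table programming. The form already records the level, so no protocol amendment or new data collection is required.

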6.5. Subset Analyses

Subset analysis is not planned.

6.6. Baseline and Other Summaries and Analyses

6.6.1. Baseline Summaries

In (a) Stage 1, (b) Stage 1, Stage 2, and Amended Stage 2, and (c) Stage 3, a breakdown of all subjects will be provided by demographic characteristics (age, race, weight, body mass index, and height), extent of disease and prior use of conventional therapy in accordance with Pfizer data standards. Mean steroid use and duration of disease will also be presented by stage. Baseline CDASI (activity and damage) will be summaried descriptively.

Subject evaluation groups will show end of study subject disposition and will show which subjects were analyzed for PK, as well as for safety (adverse events and laboratory data). Frequency counts will be supplied for subject discontinuation(s) by treatment.

6.6.2. Study Conduct and Subject Disposition

In (a) Stage 1, (b) Stage 1, Stage 2, and Amended Stage 2, and (c) Stage 3, subject evaluation groups will show end of study subject disposition and will show which subjects were analyzed in the full analysis set, and as well as for safety, PK and PD. Frequency counts will be supplied for subject discontinuations by treatment. Disposition will also be summarized separately for subjects who discontinue.

Data will be reported in accordance with reporting standards.

6.6.3. Study Treatment Exposure

In (a) Stage 1, (b) Stage 1, Stage 2, and Amended Stage 2, and (c) Stage 3, number of the doses of active and control treatments will be recorded and summarized by the treatment group.

6.6.4. Concomitant Medications and Non-Drug Treatments

All concomitant medication(s) as well as non-drug treatment(s) will be provided in the listings. These will be listed for both stages and stage will be indicated. A separate listing may be provided for DM-related prior and concomitant medications. Additional plots may be provided that illustrate concomitant medication use prior to and during the study period.

6.7. Safety Summaries and Analyses

The safety will be monitored over the study period that includes treatment and follow-up periods in all stages.

6.7.1. Adverse Events

It should be recognized that most studies are not designed to reliably demonstrate a causal relationship between the use of a pharmaceutical product and an adverse event or a group of adverse events. Except for select events in unique situations, studies do not employ formal adjudication procedures for the purpose of event classification. As such, safety analysis is generally considered as an exploratory analysis and its purpose is to generate hypotheses for further investigation. Separate AE tables will show the data from (a) Stage 1, (b) Stage 1, Stage 2, and Amended Stage 2, and (c) Stage 3.

